## 2.3.1. Risk Assessment

Allergic reaction		Eligibility criteria for
Viral infection	Antibody titer criterion for	patients
Plasma may not be effective	critical level of functional antibodies	
Based on studies in animals with vaccines against SARS-CoV-2. there is a theoretical risk of antibody dependent disease enhancement (ADE) associated with antibodies against the S protein (deAlwis et al 2020)		

## 2.3.2. Benefit Assessment

Convalescent plasma is not proven to provide any benefit for treatment of COVID-19. Potential benefit of receiving convalescent plasma during the study duration is to reduce the mortality, severity of disease and/or shorten the time of treatment for COVID-19 patients.

Participation in this study will hopefully lead to the determination of the safety and efficacy of convalescent plasma for treatment of COVID-19, and hence can inform the health authorities' decision to recommend plasma treatment for wider use. This can potentially save lives and reduce the need for infection prevention control measures targeted on reducing transmission to ultimately prevent the most vulnerable groups at risk for contracting COVID-19 disease

## 2.3.3. Overall Benefit: Risk Conclusion

Taking into account the measures taken to minimize risk to participants participating in this study, the potential risks identified in association with COVID-19 convalescent plasma are justified by the anticipated benefits that may be afforded to participants with COVID-19.

# **3. Objectives and Endpoints**

Objectives	Endpoints
Primary	
Assess the effect of convalescent plasma on mortality in COVID-19	Primary endpoint: All-cause mortality within the first 28 days of observation. Secondary endpoints: All-cause mortality within 60 days of observation.
Secondary	
Effect of convalescent plasma on recovery time in patients with active COVID-19 infection	Time from intervention to negative SARS-CoV-2 PCR during a 28 day observation period
Effect of convalescent plasma on clinical progression of COVID-19 disease	Requirement of oxygen therapy at days 1, 3, 7, 14, 21 and 28 compared to baseline Change in NEWS score at days 1, 3, 7, 14, 21 and 28 compared to baseline
Exploratory	
Effect of convalescent plasma on biomarkers in COVID-19	Change in CRP and lymphocyte count at day 1, 3, 7 and 14 in the study period. Time to normalized CRP and lymphocyte count
Safety of convalescent plasma in COVID-19	Incidence of adverse events

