## **Objectives and endpoints**

Objectives	Endpoints
Primary	
Assess the effect of convalescent plasma on mortality in COVID-19	Primary endpoint: All-cause mortality within the first 28 days of observation. Secondary endpoints: All-cause mortality within 60 days of observation.
Secondary	
Effect of convalescent plasma on recovery time in patients with active COVID-19 infection	Time from intervention to negative SARS-CoV-2 PCR during a 28 days observation period.
Effect of convalescent plasma on clinical progression of COVID-19 disease	Requirement of oxygen therapy at days 1, 3, 7, 14, 21 and 28 compared to baseline. Change in NEWS score at days 1, 3, 7, 14, 21 and 28 compared to baseline.
Exploratory	
Effect of convalescent plasma on biomarkers in COVID-19	Change in CRP and lymphocyte count at day 1, 3, 7 and 14 after intervention. Time to normalized CRP and lymphocyte count.
Safety of convalescent plasma in COVID-19	Incidence of adverse events.

Brief Summary:	The objective of this study is to evaluate the safety and efficacy of convalescent plasma treatment in symptomatic elderly COVID-19 patients in Norwegian care homes. Approximately 500 eligible participants will randomly
	allocated to either the intervention (Convalescent plasma and standard care) or control (standard care only) group in a 1:1 ratio. Participants will be followed up over a 60-day observation period.
Intervention Group and Duration:	Participants randomized to treatment group will receive convalescent plasma treatment within 2 days after randomization. They will be followed up for 60 days.
Data Monitoring Committee:	Yes
Project leader	[name], Oslo University Hospital
National coordinating institution:	Oslo University Hospital
Study sites:	Study sites are defined as the care home department of participating municipalities
Study monitor:	Clinical trial unit (CTU), Oslo University Hospital
Study setting:	Norwegian care homes for elderly patients in participating municipalities
Inclusion and exclusion criteria	
 
Inclusion criteria
 
1. Age >50 years
 
2. SARS-CoV-2 PCR positive in respiratory tract sample within 3 days before inclusion
 
3. Onset of symptoms within 7 days before intervention as assessed by the attending clinician,
 
4. Voluntary, informed and documented consent by patient or guardian
 

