	Randomization and plasma transfusion will take place immediately after enrolment, by an ambulant transfusion team. Blood samples will be taken at day 0, 1, 3, 7 and 14 in the study period. Oropharynx samples will be taken at day 0, 1, 3, 7, 14, 21 and 28 in the study period.	

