# 1.2. Schedule of Activities (SoA)

[figure not shown]
Procedure	Screening (up to intervention	Inter vention (day 0)		0	bserva	tion Peri	od (day	1-60)	
	day)	0	1	3	7	14	21	28	60
Informed consent	Х								
Inclusion and exclusion criteria	Х								
Randomization	Х								
Demography	Х								
Height and weight	Х								
Medical status and co- morbidities	Х								
Current medication	Х								
Blood samples*		X	Х	Х	Х	Х			
Oropharynx samples**		X	Х	Х	Х	Х	Х	Х	
Clinical assessment***		X	Х	Х	Х	Х	Х	Х	
Mortality registration								X	Х
Study intervention (plasma transfusion)		X							
AE and SAE review									Х

Activities are scheduled as presented in table and flow-chart below.

\* Blood: Hemoglobin, thrombocytes, leukocytes with differential count, CRP, anti-Spike IgG.

\*\*Oropharynx: RTPCR SARS-CoV-2.

\*\*\* Registration of oxygen therapy at all care homes, NEWS score where implemented in the care home routines.

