## 4. Study Design

## 4.1. Overall design

The *Norwegian convalescent plasma in COVID-19 study* is an unblinded randomized controlled trial investigating the effects of convalescent plasma on the clinical course of disease in patients with active COVID-19.

Patients referred to or staying at nursing homes with newly diagnosed symptomatic COVID-19 infection and a positive SARS-CoV-2 PCR in a respiratory tract sample will be randomized 1:1 to be given:

-Local standard supportive treatment alone

OR

-Local standard supportive treatment AND a single dose of COVID-19 convalescent plasma transfusion

Participants will be followed up on-site for up to 28 days by clinical assessments, respiratory tract sampling for SARS-CoV-2 PCR and biochemical testing at a pre-specified schedule. Participants will be followed up remotely for up to 60 days after intervention to assess mortality.

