## 5.1. Inclusion criteria

- 1. Age >50 years
- 2. SARS-CoV-2 PCR positive in respiratory tract sample within 3 days before intervention
- 3. Onset of symptoms within 7 days before intervention as assessed by the attending clinician
- 4. Volunteered, informed and documented consent by patient or guardian.

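### No common time zero is defined: day 0 and the PCR endpoint start at the transfusion, which controls never have and plasma patients may get up to 2 days after randomisation

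*Protocol*

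**What the plan says.** Several parts of the protocol tie the clock to the transfusion:

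- **Section 3 (and the synopsis):** the recovery endpoint is "Time from intervention to negative SARS-CoV-2 PCR during a 28 day observation period".
- **Section 1.2, Schedule of Activities:** the intervention is day 0, observation is day 1 to day 60, and randomisation is marked in the screening column.
- **Section 4.1:** "Participants will be followed up remotely for up to 60 days after intervention to assess mortality". The same section gives controls standard supportive treatment only.
- **Section 8.3.1:** SAE collection begins when the intervention starts.

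The protocol is not consistent on how long after randomisation the transfusion comes. The synopsis entry on intervention group and duration says: "Participants randomized to treatment group will receive convalescent plasma treatment within 2 days after randomization". The synopsis entry on participants' timeframe says: "Randomization and plasma transfusion will take place immediately after enrolment, by an ambulant transfusion team". Section 7.1 has the transfusion follow directly on consent.

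The PCR eligibility window also has two anchors. Section 5.1 requires "SARS-CoV-2 PCR positive in respiratory tract sample within 3 days before intervention"; the synopsis requires "SARS-CoV-2 PCR positive in respiratory tract sample within 3 days before inclusion". Both places count the symptom window back from intervention.

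The primary endpoint does not name the transfusion. Section 3 counts 28 days of observation and Section 9.3.3 counts 28 days of follow-up, and neither gives a starting event.

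**The concern.** A randomised comparison of times to an event needs the same starting point in both arms, fixed no later than allocation. Here the stated starting point happens in one arm only, and it happens after allocation. For controls the recovery endpoint has no start date, and the numbered visit days for oxygen, NEWS and PCR have no anchor.

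Whoever builds the dataset will have to supply a date. The obvious choice for controls is the randomisation date. If plasma patients are still counted from transfusion, as the endpoint wording says, each plasma patient's time is shortened by the wait for plasma. Plasma then appears to speed clearance when it does nothing. The trial is open label, and the time of transfusion depends on logistics and on the patient's condition. It is therefore a poorer time zero than randomisation even where the delay is short.

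**Working it through.** **1. The plan's own figures.** Inputs from Section 9.2: 30% against 18% mortality, hazard ratio 0.60, 80% power, 5% level (taken as two-sided), 1:1 allocation.

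- Schoenfeld events: (1.960 + 0.842)² / (0.25 × (ln 0.60)²) = 120.3, so 121.
- Patients: 120.3 / 0.24 = 501.3, so 502, where 0.24 is the mean of 0.30 and 0.18.
- With the interim inflation: 502 × 1.008 = 506, or 253 per arm.

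The protocol's 121, 502 and 506 are reproduced. None of them depends on the time origin, so a common clock leaves them unchanged.

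**2. Time to negative PCR with unequal clocks and no true effect.** Inputs from the protocol: 253 per arm; visits at days 1, 3, 7, 14, 21 and 28 (Schedule of Activities; Section 8.1 omits day 21); delay between 0 and 2 days. Assumptions not in the protocol: Weibull clearance with median 10, 14 or 18 days and shape 1, 1.5 or 2, and no competing deaths. Controls are timed from randomisation; plasma patients have the delay subtracted. Clearance is recorded at the next scheduled visit, and the arms are compared by a two-sided 5% log-rank test. There were 1,500 simulated trials per cell. Rejection rates:

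| Median (days) | Shape | No delay | 1-day delay | 2-day delay |
|---|---|---|---|---|
| 10 | 1.0 | 4.9% | 14.4% | 40.3% |
| 10 | 1.5 | 5.9% | 25.2% | 75.8% |
| 10 | 2.0 | 4.7% | 46.1% | 96.1% |
| 14 | 1.0 | 5.0% | 10.8% | 27.2% |
| 14 | 1.5 | 5.5% | 16.1% | 47.4% |
| 14 | 2.0 | 4.7% | 24.6% | 76.5% |
| 18 | 1.0 | 4.4% | 8.8% | 19.5% |
| 18 | 1.5 | 3.4% | 12.3% | 32.3% |
| 18 | 2.0 | 5.1% | 16.9% | 52.0% |

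A delay drawn uniformly over 0 to 2 days has a mean of 1 day and gives about 9% to 45% over the same grid, close to the 1-day column. In repeat runs the lowest 2-day cell fell between about 17% and 20%, so that range is stated as about 17% to 96%. With a delay, nearly all rejections favour plasma.

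**3. Mortality with unequal clocks and no true effect.** Take 30% 28-day mortality and a constant hazard: λ = −ln(0.70)/28 = 0.01274 per day.

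- Deaths in a 2-day gap: 1 − exp(−2λ) = 2.5%, or 0.0252 × 253 = 6.4 plasma patients. For a 1-day gap: 1.3%, or 3.2 patients.
- If the deaths in a 2-day gap were left out of the count but the patients kept in the denominator, plasma mortality would read 0.30 × (1 − 0.0252) = 29.3% against 30%, a ratio of 0.975.

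On the event-rate scale, with a uniform 0 to 2 day delay and pre-transfusion deaths outside observation, the plasma-to-control ratio depends on the shape of the hazard:

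| Weibull shape | 0.6 | 0.8 | 1.0 | 1.5 | 2.0 |
|---|---|---|---|---|---|
| Rate ratio | 0.88 | 0.96 | 1.00 | 1.05 | 1.07 |

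A falling hazard favours plasma and a rising one goes against it. The protocol gives no figure from which to choose the shape.

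**The case against.** The strongest reply is that the protocol never gives the arms different clocks. The Schedule of Activities does not limit the day-0 samples and assessments to one arm, and Section 8.4 says samples come from all participants, so controls do have a day-0 visit. This is right, and it is why the point is that a common time zero is missing. But the visit has no date rule for controls, and the PCR endpoint names an event that they lack.

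It can also be said that transfusion is in practice immediate and 2 days is only an outer limit, since the ambulatory team both randomises and delivers plasma (Sections 6.2 and 6.3). If so, the bias shrinks towards nothing. The protocol nevertheless states both timings, and an average delay of 1 day already matters for the PCR endpoint.

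Two stronger readings are tempting, and the document does not support them.

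- **Built-in immortal time in the mortality comparison.** A reader might infer that plasma-arm deaths before transfusion are lost. The primary endpoint does not name the transfusion. The full analysis set is as randomised (Section 9.3.2). Vital status is sought for every randomised patient, treated or not (Section 7.3), and deaths come from the national registry (Section 8.1). Even if such deaths were lost, the direction of the bias would be unknown.
- **Eligibility lapsing after randomisation in the plasma arm only.** A reader might infer this from the windows in Section 5.1. Eligibility is checked in screening (Section 1.2), eligible patients are randomised (Section 9.3.1), and nothing removes a late-transfused patient from the full analysis set.

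**Conclusion.** The concern holds for the recovery endpoint. As worded, time to negative PCR is undefined in the control arm. The most likely workaround raises the false-positive rate from about 5% to about 9% to 45% with a uniform 0 to 2 day delay, and to about 17% to 96% if every plasma patient waits 2 days. These sizes rest on assumed clearance medians and shapes, and on controls being timed from randomisation while plasma patients are timed from transfusion. The protocol does not prescribe that pairing, but it does not rule it out.

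Oxygen and NEWS are less exposed, because they are compared with baseline on numbered days, but those days have no anchor for controls either. For 28- and 60-day mortality the start should be stated, but the expected effect is small, of uncertain direction and largely guarded by the as-randomised analysis set, the vital-status search and the registry. This point is no ground for calling the primary comparison biased.

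**What to change.** 1. Define day 0 as the date and time of randomisation in both arms, for every efficacy endpoint, every numbered visit day and the 28- and 60-day mortality windows. Amend the synopsis, Section 1.2, Section 3 and Section 4.1 to match, and move randomisation to the day-0 column of the schedule.
2. Reword the recovery endpoint as time from randomisation to negative SARS-CoV-2 PCR.
3. Record the date and time of transfusion as an exposure variable only, not as a clock.
4. State in Section 8.3.1 when SAE collection starts for a control patient.
5. Reconcile the synopsis statement allowing up to 2 days with the synopsis statement of immediate transfusion and with Section 7.1. Reconcile the PCR window, counted from inclusion in the synopsis and from intervention in Section 5.1. Which timing and which window apply is a clinical decision for the sponsor and is not proposed here.

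The cost is wording. The 121 deaths and 502 (506) patients do not change. The one drawback is that plasma-arm visit days shift relative to the transfusion by at most the transfusion delay.

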## 4. Study Design

## 4.1. Overall design

The *Norwegian convalescent plasma in COVID-19 study* is an unblinded randomized controlled trial investigating the effects of convalescent plasma on the clinical course of disease in patients with active COVID-19.

Patients referred to or staying at nursing homes with newly diagnosed symptomatic COVID-19 infection and a positive SARS-CoV-2 PCR in a respiratory tract sample will be randomized 1:1 to be given:

-Local standard supportive treatment alone

OR

-Local standard supportive treatment AND a single dose of COVID-19 convalescent plasma transfusion

Participants will be followed up on-site for up to 28 days by clinical assessments, respiratory tract sampling for SARS-CoV-2 PCR and biochemical testing at a pre-specified schedule. Participants will be followed up remotely for up to 60 days after intervention to assess mortality.

# 4.2. Scientific rationale for study design

Innate and adaptive immune responses play a central role in combating viral infections like COVID-19. The innate immune system represents an immediate and first frontline that sets the stage for a more advanced and specific adaptive immune response that typically arises some days later. This adaptive immune response includes the production of increasingly specific antibodies in the form of immunoglobulins M and G (IgM and IgG, respectively) directed towards the invading culprit. These immunoglobulins thus represent an end product and the pinnacle of the immunological response, capable of destroying the invading microbe both directly and indirectly. Immunoglobulins are furthermore a central part of immunological memory, i.e. the ability of the immune system to "remember" an invading pathogen and mount a swift and powerful response to a second challenge. Administering specific antibodies to an individual with no immunological memory to the pathogen – either in the form of vaccines (like hepatitis A, hepatitis B) or therapeutically (like Varicella, Rabies, hepatitis B) - mimics this memory and gives the patient a well-documented advantage in fighting off the infection. The injected antibodies give the adaptive immune system a head-on start even as it starts to produce its own antibodies.

Immunoglobulins constitute a major part of human plasma, and plasma will therefore include specific antibodies towards a wide range of pathogens, including both bacteria and virus. The composition and relative abundance of this antibody repertoire will vary between individuals, but a major feature will be relatively high levels of antibodies towards recently encountered microbes and infections. The use of serum or plasma from recently immunized individuals (or horses) that contain high levels of relevant antibodies to treat newly infected individuals have a long tradition in human medicine but few studies have actually tested the effect in a rigorous manner.

COVID-19 disease elicits varying degree of both innate and adaptive immune response in infected patients. Preliminary reports suggests there is an initial delay of innate antiviral mechanisms leaving the SARS-CoV-2 virus with an extended replicative phase of typically 3-5 days before the patient's immune system reacts properly and the patient enters a symptomatic stage that can include fever, cough, dyspnea, rhinorrhea, diarrhea, nausea and abdominal pain. The adaptive immune response to SARS-CoV-2 is poorly understood with a striking variability in the production of specific antibodies that seem related to the degree of symptomatic disease, while the nature of adaptive cellular responses is characterized by a pan-T cell depletion. Specific SARS-CoV-2 antibodies have been detected as early as the first week after debut of symptoms in moderately and severely ill patients with the prevalence of seropositivity gradually increasing to 100 % after 3 weeks.

Recent case reports or case series from China, with the inherent bias of small sample size and open, non-controlled clinical trials, indicated no major safety issues. It was not possible to elucidate any effect of plasma on the course of disease, due to concomitant therapy with other drug interventions (Duan et al 2020, Shen et al 2020). A matched control study in US patients showed benefit in non-intubated patients (Sean et al, 2020). The first randomized clinical study in China was terminated due to lack of effect in late stages (Li et al, 2020), but potential benefits were also reported (Casadevall, Joyner & Pirofski, 2020).

There is however a strong scientific rationale for testing the efficacy of convalescent plasma in treatment of COVID-19 patients, and this study is designed to maximize the effect of the plasma by including patients in an early stage of the disease.

## 4.3 Justification for dose

The suggested dosing of SARS-CoV-2 convalescent plasma for transfusion is 1 unit; ~200-350 mL. This is based on the volume of available plasma drawn from donors in one unit, and from a prior study of SARS-CoV-1 patients in 2005 showing clinical benefit at median 291 mL plasma administered per patient.

# 4.4 End of study definition

The end of the study is defined as the date of the last visit of the last participant in the study.

CONFIDENTIAL

A participant is considered to have completed the study if he/she has completed all procedures of the study including the last visit.

## 5. Study Population

The target population for this study is individuals above the age of 50 in early stages of COVID-19 disease. Participants will be recruited from municipal healthcare institutions that admit and care for symptomatic COVID-19 patients in need of medical care but not referred to hospitals.

In Norway, around 15% of the population is aged 67 years or more. In 2018, around 32200 persons were living in care homes for the elderly on long term basis, and an additional 9000 persons on time-limited stays.

Data on COVID-19 in Norway showed that at end of April 2020, among the total 204 deaths in the population reported, 60% were among patients in institutions outside hospitals, and 89% of the total 204 deaths were persons aged 70 years or more (FHI.no).

The population in care homes has a high proportion of dementia and co-morbidities, which both are significant factors to take into account in the study implementation and outcome analysis. In particular, the presence of dementia represents a challenge for the consent to participate which will need to be handled by the patient's guardian if such is appointed, acting in the best interest of the patient.

## 5.1. Inclusion criteria

- 1. Age >50 years
- 2. SARS-CoV-2 PCR positive in respiratory tract sample within 3 days before intervention
- 3. Onset of symptoms within 7 days before intervention as assessed by the attending clinician
- 4. Volunteered, informed and documented consent by patient or guardian.

## 5.2. Exclusion criteria

- 1. Included in any other RCT
- 2. Allergic reactions to plasma products
- 3. Acute severe co-morbidity
- 4. Estimated life-expectancy <90 days prior to COVID-19 as assessed by the attending clinician.
- 5. Other reasons where the attending clinician deems trial participation to be against the best interest of the patient

## 5.3. Study Intervention and Concomitant Therapy

Convalescent plasma will be collected from volunteer non-paid donors who recovered from a CoV-2 infection. Collection volume will be split to therapeutic units of 200-300 ml. Previous medical therapy will be continued with no interruption.

	Т		
ARM Name	COVID-19 convalescent plasma		
Intervention	ISBT E9735 CONVALESCENT PLASMA CPD/XX/<=-18C COVID-19		
Name	ISBT E9736 Apheresis CONVALESCENT PLASMA CPD/XX/<=-18C COVID-19		
	ISBT E9754 Apheresis CONVALESCENT PLASMA ACD-A/XX/<=-18C 1st container COVID-19		
	ISBT E9755 Apheresis CONVALESCENT PLASMA ACD-A/XX/<=-18C 2nd container COVID-19		
	ISBT E9756 Apheresis CONVALESCENT PLASMA ACD-A/XX/<=-18C 3rd container COVID-19		
	ISBT E9757 Apheresis CONVALESCENT PLASMA ACD-A/XX/<=-18C 4th container COVID-19		
Туре	Biologic		
Dose Formulation	200-300 ml		
Unit Dose Strength(s)	High titer, defined as virus neutralization assay titer >1:160 or equivalent in accordance with EBA (to be confirmed)		
Dosage Level(s)	1 dose at inclusion		
Route of Administration	I.V. transfusion		
Use	Clinical indication		
IMP and NIMP	Investigational Medicinal product (IMP)		
Sourcing	COVID-19 convalescent plasma from voluntary non-paid donors at the following Norwegian blood banks: Oslo University Hospital, Haukeland University Hospital, St. Olav's Hospital		
Packaging and Labeling	Following local SOP for plasma-labeling, using the correct ISBT code		

